Approximately 80 subjects will be randomized 1:1:1:1 (approximately 20 per arm) to receive one of the listed study medications with a sufficient quantity of a non-alcoholic beverage to enable swallowing of the capsules:

- 1) CTAP101 Capsules 60 mcg once daily outside of the phase 1 unit at bedtime, except on Days 1 and 29 when dosing will occur in the phase 1 unit in the morning before breakfast.
- 2) IR calcifediol 266 mcg in the phase 1 unit before breakfast on the mornings of Day 1 and Day 29.
- 3) Cholecalciferol 300,000 IU (high-dose) in the phase 1 unit before breakfast on the mornings of Day 1 and Day 29.
- 4) Paricalcitol 1 mcg plus cholecalciferol 800 IU (low-dose) once daily outside of the phase 1 unit in the morning before breakfast, except on the mornings of Days 1 and 29 when dosing will occur in the phase 1 unit before breakfast.

After 4 weeks of treatment, subjects who are receiving paricalcitol will double the dose to 2 mcg plus cholecalciferol 800 IU once daily in the morning before breakfast provided that (a) the plasma iPTH has not decreased by at least 30% from pretreatment BL and remains above 70 pg/mL, (b) corrected serum calcium is <9.8 mg/dL, and (c) serum phosphorus is <5.5 mg/dL. Subjects who are receiving CTAP101 Capsules, IR calcifediol or cholecalciferol (300,000 IU) will not undergo upward dose titration.

Subjects will reduce the dose of study medication per the schedule below in the event that plasma iPTH is confirmed to be <30 pg/mL, corrected serum calcium is confirmed to be >10.3 mg/dL, or serum phosphorus is confirmed to be >5.5 mg/dL. Subjects will suspend dosing if plasma iPTH is confirmed to be <15 pg/mL or corrected serum calcium is confirmed to be >11.0 mg/dL, and will resume dosing when plasma iPTH is ≥30 pg/mL and corrected serum calcium is <9.8 mg/dL per the dose schedule below.

Dose reduction (if needed):

CTAP101: decrease to 30 mcg per day (from 60 mcg per day)

IR calcifediol: hold Day 29 dose

Cholecalciferol 300,000 IU: hold Day 29 dose

Paricalcitol: decrease dose to 1 mcg per day (from 2 mcg per day)

Cholecalciferol 800 IU will not be adjusted

In the event that a dose reduction is required for a subject receiving the minimum dosage of CTAP101 Capsules (30 mcg per day) or paricalcitol (1 mcg per day), the subject will suspend dosing and resume when iPTH is ≥ 30 pg/mL and corrected serum calcium is <9.8 mg/dL at the same minimum dosage.

Dose resumption (if needed):

CTAP101: 30 mcg per day

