2.2 Study Endpoints

2.2.1 *Pharmacokinetic Endpoints*

The following PK parameters will be calculated using observed and BL-adjusted serum calcifediol **CCI** [REDACTED] concentrations: AUC, C_{max} , t_{max} , steady-state concentration (C_{ss}), time to steady-state concentration (t_{ss}), terminal elimination half-life ($t_{1/2}$), clearance (CL/F), and volume of distribution (Vd/F), as feasible.

CCI [REDACTED]

2.2.3 *Primary Safety Endpoints*

Safety and tolerability of each medication will be evaluated in the Safety population by AEs, physical examinations (PEs), vital signs (VS), hematology and clinical chemistries.

2.2.4 *Secondary Safety Endpoints*

Secondary safety endpoints will include incidence of hypercalcemia and drug-related hyperphosphatemia. The number (n, %) of subjects with hypercalcemia (two consecutive visits with serum calcium greater than 10.3 mg/dL) or hyperphosphatemia (two consecutive visits with serum phosphorus greater than 5.5 mg/dL) will be calculated.

2.2.5 *Efficacy Endpoints*

This study is descriptive and no primary or secondary efficacy endpoints are defined. Descriptive analysis and plots for the ITT and PP populations will be created of serum calcifediol, **CCI** [REDACTED]

[REDACTED] [REDACTED] [REDACTED] [REDACTED] [REDACTED] [REDACTED] which will be specified in an accompanying statistical analysis plan (SAP).

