4.2 Inclusion Criteria

Each subject must meet the following criteria to be enrolled in this study:

1. Be at least 18 years of age.
2. Have stage 3 or 4 CKD (eGFR of ≥ 15 to <60 mL/min/1.73m² using the Modification of Diet in Renal Disease equation).
3. Be without any disease state or physical condition that might impair evaluation of safety and efficacy or which, in the Investigator's opinion, would interfere with study participation, including:
 - a. Serum albumin ≤ 3.0 g/dL;
 - b. Serum transaminase (alanine transaminase, glutamic pyruvic transaminase, aspartate aminotransferase or glutamic oxaloacetic transaminase) > 2.5 times the upper limit of normal at screening; and,
 - c. Urinary albumin excretion >3000 μ g/mg creatinine.
4. Exhibit during the initial Screening Visit:
 - a. Plasma iPTH ≥ 65 pg/mL and <400 pg/mL if receiving calcitriol or other 1 α -hydroxylated vitamin D analog (paricalcitol or doxercalciferol); or
 - b. Plasma iPTH ≥ 85 pg/mL and <500 pg/mL if not receiving calcitriol or other 1 α -hydroxylated vitamin D analog;
 - c. Serum total 25-hydroxyvitamin D <30 ng/mL, unless taking vitamin D supplementation (including multivitamins and fish oil); and,
 - d. If taking calcitriol or another 1 α -hydroxylated vitamin D analog, subjects must forgo treatment with these non-study agents for the duration of the study and undergo a 4-week washout period and meet inclusion criterion 5.
 - e. For subjects who are taking vitamin D supplementation (including multivitamins or fish oil), they must forgo treatment with these non-study agents for the duration of the study. If the serum 25-hydroxyvitamin D level is <30 ng/mL, there is no need for the subjects to complete a washout period as a result of vitamin D supplementation. If, however, serum 25-hydroxyvitamin D level is ≥ 30 ng/mL, the subjects must undergo a 4-week washout period and meet inclusion criterion 5. If at the end of 4 weeks of washout, the 25 hydroxyvitamin D level is still ≥ 30 ng/mL, the washout may be extended by up to another four weeks for a total of 8 weeks.
5. Exhibit after the washout period (if required):
 - a. Plasma iPTH ≥ 85 pg/mL and <500 pg/mL;

- b. Corrected serum calcium <9.8 mg/dL; (corrected for serum albumin)
- c. Serum total 25-hydroxyvitamin D <30 ng/mL; and,
- d. Serum phosphorus <5.5 mg/dL.
6. If taking more than 1,500 mg/day of elemental calcium, reduce calcium use (to approximately 1,000 to \leq 1,500 mg/day) for the duration of the study.

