5.3 Dose Reduction Criteria

Subjects will reduce the dose of medication at any time by the schedule below in the event that plasma iPTH is confirmed to be <30 pg/mL, corrected serum calcium is confirmed to be >10.3 mg/dL, or serum phosphorus is confirmed to be >5.5 mg/dL. Subjects will suspend dosing if plasma iPTH is confirmed to be <15 pg/mL or corrected serum calcium is confirmed to be >11.0 mg/dL, and will resume when plasma iPTH is \geq 30 pg/mL and corrected serum calcium is <9.8 mg/dL per the dose schedule below.

Dose reduction:

CTAP101: decrease to 30 mcg per day (from 60 mcg per day)

IR calcifediol: hold Day 29 dose

Cholecalciferol 300,000 IU: hold Day 29 dose

Paricalcitol: decrease dose to 1 mcg per day (from 2 mcg per day).

Cholecalciferol 800 IU will not be adjusted during the study period

In the event that a dose reduction is required for a subject receiving the minimum dosage of CTAP101 Capsules (30 mcg per day) or paricalcitol (1 mcg per day), the subject will suspend dosing and resume when iPTH is \geq 30 pg/mL and corrected serum calcium is <9.8 mg/dL at the same minimum dosage.

Dose resumption:

CTAP101: 30 mcg per day

Paricalcitol: 1 mcg per day

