Subjects will suspend dosing if plasma iPTH is confirmed to be <15 pg/mL or corrected serum total calcium is confirmed to be >11.0 mg/dL, and will resume dosing when plasma iPTH is  $\geq$ 30 pg/mL and corrected serum total calcium is <9.8 mg/dL per the following schedule. In the event that a dose reduction is required for a subject receiving the minimum dosage of CTAP101 Capsules (30 mcg per day) or paricalcitol (1 mcg per day), the subject will suspend dosing and resume when iPTH is  $\geq$ 30 pg/mL and corrected serum total calcium is <9.8 mg/dL at the same minimum dosage.

Dose resumption (if needed):

CTAP101: 30 mcg per day

Paricalcitol 1 mcg per day

The subjects will be housed in a phase 1 unit for approximately 14 to 26 hours at the beginning of the study and on study Day 29 to provide the blood samples required for a detailed determination of the PK profiles for serum calcifediol [REDACTED]

[REDACTED] Blood samples for some of the PK and [REDACTED] assessments will be collected in the phase 1 unit at -2, 0, 2, 4, 6, and 12 hours, either in the phase 1 unit or during an outpatient visit at 24 hours, during the outpatient visit at 48 hours, and then weekly following the first dose and the Day 29 dose of study drug. Blood samples for other [REDACTED] assessments will be collected at less frequent intervals. Urine collections (over 24 hours) will be obtained at pretreatment BL (Visits 2 and 3), starting immediately after dosing on Day 1 (Visit 4) and Day 29 (Visit 10), and at the end of study (EOS) visit

(Visit 16) or at early termination (ET). The full schedule of assessments is provided in Table 1.

Subjects receiving treatment with calcitriol or another 1 $\alpha$ -hydroxylated vitamin D analog, or if serum total 25D >30 ng/mL when taking vitamin D supplementation (including multivitamins and fish oil), will complete a 4-week washout period before BL assessments. Subjects will forgo further dosing with these nonstudy drugs for the duration of the study. Subjects receiving calcimimetic therapy within the 12 weeks preceding Screening will be ineligible for enrollment.

Blood samples will be collected from all subjects at weekly intervals during the screening and BL periods, during the 8-week treatment period, and at the specified times during the PK/CCI assessment. Key parameters to be analyzed in the collected samples include some or all of the following: serum calcifediol, CCI [REDACTED]

[REDACTED] serum 24,25D3, CCI [REDACTED]

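### The resumption rules never test phosphorus, so a minimum-dose suspension for phosphorus above 5.5 mg/dL can end with phosphorus still above 5.5

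*Protocol*

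**What the plan says.** Protocol section 5.3 lists three triggers for dose reduction, any one of which is sufficient: confirmed iPTH below 30 pg/mL, confirmed corrected calcium above 10.3 mg/dL, "or serum phosphorus is confirmed to be >5.5 mg/dL". Dosing is suspended outright for confirmed iPTH below 15 pg/mL or corrected calcium above 11.0 mg/dL.

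Two sentences govern restarting:

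- **General sentence**, after an outright suspension: resume when iPTH is at least 30 pg/mL "and corrected serum calcium is <9.8 mg/dL per the dose schedule below". That schedule restarts CTAP101 at 30 mcg and paricalcitol at 1 mcg.
- **Minimum-dose sentence**, for a subject already on CTAP101 30 mcg or paricalcitol 1 mcg who needs a reduction: "the subject will suspend dosing and resume when iPTH is" at least 30 pg/mL "and corrected serum calcium is <9.8 mg/dL at the same minimum dosage".

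The synopsis carries the same pair (its minimum-dose sentence begins "In the event that a dose reduction is required for a subject receiving the minimum dosage"), and so does SAP section 3.3, whose general sentence reads "and corrected serum total calcium is <9.8 mg/dL per the following schedule". No other section of either document gives a phosphorus level for restarting.

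**The concern.** A stopping rule needs a release condition tied to whatever caused the stop. iPTH and calcium each have one; phosphorus does not. Read literally, the rule allows a subject stopped for high phosphorus to restart with phosphorus unchanged, in some cases at once.

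The same level matters elsewhere. Protocol section 2.2.4 counts "hyperphosphatemia (two consecutive visits with serum phosphorus greater than 5.5 mg/dL") as a secondary safety event, although it introduces that endpoint as drug-related. Section 5.3.1 names hyperphosphatemia as an effect of excess dosing, and section 5.5.1 prohibits phosphate binders, so withholding drug is the main response the protocol itself defines. Sites could also handle the same result differently, which would make exposure in the dose-adjusted subgroups of SAP sections 7.1 and 7.2 less uniform.

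**Working it through.** The plan gives no figure to reproduce, so the check sets the rules side by side and looks for their overlap.

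**Inputs (Protocol section 5.3)**

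| Measure | Triggers reduction | Triggers outright suspension | Required to resume (both sentences) |
|---|---|---|---|
| iPTH, pg/mL | <30 | <15 | ≥30 |
| Corrected calcium, mg/dL | >10.3 | >11.0 | <9.8 |
| Phosphorus, mg/dL | >5.5 | none | none |

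**Logic at the minimum dose**

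- Suspend if iPTH <30, or calcium >10.3, or phosphorus >5.5.
- Resume if iPTH ≥30 and calcium <9.8.

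The resume condition rules out the first two suspension triggers. Both rules can therefore be met together only when phosphorus is >5.5, iPTH is ≥30 and calcium is <9.8. With phosphorus <5.5 added to the resume condition, no such overlap remains.

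**Worked cases** (illustrative values, not from the documents)

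| State | iPTH | Calcium | Phosphorus | As written | With phosphorus <5.5 added |
|---|---|---|---|---|---|
| Minimum dose, low iPTH | 25 | 9.3 | 4.5 | stays off | stays off |
| Minimum dose, high calcium | 100 | 10.5 | 4.5 | stays off | stays off |
| Minimum dose, high phosphorus | 100 | 9.3 | 6.0 | resumes on the same sample | stays off |
| Minimum dose, high phosphorus | 100 | 10.0 | 6.0 | waits for calcium | stays off |
| Same subject later | 100 | 9.7 | 6.0 | resumes | stays off |
| Suspended for calcium >11.0, later | 60 | 9.6 | 6.0 | resumes | stays off |
| Suspended for iPTH <15, later | 35 | 9.4 | 6.0 | resumes | stays off |
| Suspended for calcium >11.0, later | 60 | 9.6 | 5.0 | resumes | resumes |

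**Grid check.** Take iPTH 10, 20, 30, 60, 100; calcium 9.0, 9.7, 9.8, 10.0, 10.3, 10.4, 11.1; phosphorus 5.0, 5.5, 5.6, 6.5.

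- All combinations: 5 × 7 × 4 = 140.
- No trigger (iPTH ≥30, calcium ≤10.3, phosphorus ≤5.5): 3 × 5 × 2 = 30. The other 140 − 30 = 110 require suspension at the minimum dose.
- Phosphorus is the only trigger: 3 × 5 × 2 = 30.
- Of those 30, calcium <9.8: 3 × 2 × 2 = 12, which meet the resume rule on the same sample. Calcium 9.8 to 10.3: 3 × 3 × 2 = 18, which wait for calcium only.
- None of the other 110 − 30 = 80 states, each with an iPTH or calcium trigger, can resume on the same sample.
- With a phosphorus condition added (≤5.5, and so also the stricter <5.5), 0 of 110 resume on the same sample.

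These counts depend on the grid and show the logic; they are not frequencies in subjects.

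**Who can be affected.** Paricalcitol starts at its minimum dose, so the gap applies to about 20 subjects from Day 1, and to fewer after any doubling at Day 29. CTAP101 subjects reach 30 mcg only after a reduction or a restart. The two monthly arms have no restart dose and are outside the point. Entry requires "Corrected serum calcium <9.8 mg/dL", so same-sample release applies to any phosphorus-only subject whose calcium has stayed under its entry ceiling and whose iPTH is at least 30 pg/mL.

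**The case against.** The strongest reply is that a sensible reader would keep such a subject off drug. The text describes a sequence of suspending and then resuming, the trigger must be confirmed, and Protocol section 5.3 applies it at any time, so a subject restarted above 5.5 would meet it again. That helps only in part. If the trigger recurs, the same confirmed result requires both suspension and resumption, and neither document says which prevails. The wording about timing also appears only in section 5.3, not in the synopsis or the SAP.

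A second reply is that the general sentence concerns subjects stopped for calcium or iPTH, so phosphorus did not stop them. That is true of the cause. But the general sentence restarts them at the minimum dose, where phosphorus above 5.5 again calls for suspension, and the same conflict follows.

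Third, there are safeguards. Phosphorus is measured weekly, abnormal results count as clinically significant unless the investigator says otherwise (Protocol section 6.6.6), and the investigator may withdraw a subject for a clinically significant laboratory change (section 6.8). These limit harm, but they rest on judgement and set no restart level.

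Two points stand. Impaired kidney function can itself raise phosphorus (Protocol section 1.5), so stopping drug may not lower it. And few subjects are likely to be affected.

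**Conclusion.** The concern holds. Confirmed phosphorus above 5.5 mg/dL can stop dosing at the minimum dose, yet no resumption sentence asks for it to fall. This is a fault in a stated rule rather than a missing detail. Phosphorus is tested at entry, at paricalcitol up-titration and at dose reduction, and no reason is given for leaving it out at resumption.

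The size is minor. The number of subjects cannot be derived, because the documents give no on-treatment distribution of phosphorus or calcium. It is probably small: entry requires phosphorus below 5.5 mg/dL, treatment lasts 8 weeks, and the mean rises cited in Protocol sections 1.9 and 1.12 are about 0.1 to 0.2 mg/dL. The conclusion assumes the sentences are applied as written. It is still worth correcting, because it concerns subject safety and consistent dosing across sites.

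**What to change.** After the calcium condition, add a requirement that serum phosphorus be below 5.5 mg/dL. Make the change in both resumption sentences in Protocol section 5.3, the synopsis and SAP section 3.3: 2 × 3 = 6 sentences. The threshold matches entry (Protocol section 4.2) and paricalcitol up-titration (section 5.2). A subject at exactly 5.5 would stay off drug although 5.5 does not trigger a reduction. Calcium already works this way, with a wider margin between its trigger (>10.3) and its release level (<9.8).

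The change needs no new sample, because phosphorus is in the partial chemistry panel (SAP Table 1, footnote d). Sample size and analysis methods are unchanged, and suspensions and resumptions are already listed under SAP section 9.7. The cost is that a few subjects with persistently high phosphorus may stay off drug longer. One still suspended at Day 29 would miss that dose, which would affect the data for the Day 29 PK parameters and the exploratory comparison in SAP section 7.3.

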5.3.1 Overdose and Toxicity

Excessive administration of calcifediol, cholecalciferol, or paricalcitol can cause hypercalciuria, hypercalcemia, hyperphosphatemia, or over suppression of intact PTH. Common symptoms of vitamin D overdosage may include constipation, decreased appetite, dehydration, fatigue, irritability, muscle weakness, or vomiting.

Treatment of acute accidental overdosage with calcifediol, cholecalciferol, or paricalcitol should consist of general supportive measures. If the overdosage is discovered within a short time, induce emesis or perform gastric lavage to prevent further absorption. Obtain serial serum and

urine calcium measurements, and assess any electrocardiographic abnormalities due to hypercalcemia. Discontinue supplemental calcium. Treat with standard medical care if persistent and markedly elevated serum calcium levels occur.

5.4 Method of Assigning Subjects to Treatment Groups

After signing the ICF, prior to any study-related activities, each subject will be assigned a unique 7 digit subject identification number which will be retained throughout the study and that will be unique across all sites. The 7 digit subject identification number (SSSNNNN) will consist of a 3-digit site number (SSS) and a 4-digit subject number (NNNN) at the applicable clinical site. Should a subject be withdrawn from the study, that subject's 7 digit identification number will not be reassigned.

Randomization will be accomplished in blocks of 4 subjects in a 1:1:1:1 ratio with subjects being assigned to treatment with CTAP101 Capsules, IR calcifediol, high-dose cholecalciferol or paricalcitol plus low-dose cholecalciferol. Randomization will occur during Visit 4 provided that each subject is deemed eligible for enrollment based, in part, on laboratory assessments obtained at the preceding visit (Visit 1). Laboratory assessments obtained at Visits 2-3 will not be considered in the determination of enrollment eligibility.

In the event that a significant difference in mean baseline body weight among subjects by treatment group emerges as enrollment progresses, the randomization scheme (described immediately above) will be suspended and subjects will be assigned to a specific treatment group using the following alternative procedure:

Step 1: Calculate the mean body weight for subjects who have been previously entered into the treatment period, in aggregate and by treatment group.

Step 2: Compare the subject's body weight (measured at Visit 1) with the current mean body weight of all subjects who have previously been entered into the treatment period. If the subject's weight is equal to or higher than the current mean body weight of all previously treated subjects, then assign the subject to a treatment group (which still has less than 20 subjects) having the lowest mean body weight. If the subject's weight is lower than the current mean body weight of all previously treated subjects, then assign the subject to a treatment group (which still has less than 20 subjects) having the highest mean body weight.

Step 3 (if needed): If a subject cannot be assigned to a treatment group according to Step 2 (above) and there are fewer than 80 subjects assigned to treatment, then assign the subject to a treatment group (which still has less than 20 subjects) with the most similar mean body weight.

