An Open-Label, Repeated-Dose Safety, Efficacy, Pharmacokinetic and Pharmacodynamic Study of Oral CTAP101 Capsules, IR Calcifediol, High-Dose Cholecalciferol, and Paricalcitol Plus Low-Dose Cholecalciferol in Patients with Secondary Hyperparathyroidism, Stage 3 or 4 Chronic Kidney Disease and Vitamin D Insufficiency.

Study Number:

CTAP101-CL-4001

Study Phase: 4

Objectives:

The objectives of this study are to assess the repeated-dose safety, efficacy, pharmacokinetic (PK) **CCI** profiles of CTAP101 Capsules, IR calcifediol, high-dose cholecalciferol, and paricalcitol plus low-dose cholecalciferol in patients with secondary hyperparathyroidism (SHPT), stage 3 or 4 chronic kidney disease (CKD) and vitamin D insufficiency (VDI).

[figure not shown]
Study Design:

This is a phase 4, multi-center, 4-arm, open-label study to gather comparative data evaluating the safety, efficacy and PK **CCI** profiles for CTAP101 Capsules, IR calcifediol, high-dose cholecalciferol, and paricalcitol plus low-dose cholecalciferol to treat SHPT in male and female subjects aged at least 18 years with stage 3 or 4 CKD and VDI. The study will be conducted at multiple sites within the United States (US). Approximately 160 subjects will be screened to

enroll approximately 80 eligible subjects who will be randomized 1:1:1:1 (approximately 20 per arm, balanced for body weight) to receive 8 weeks of treatment as follows: CTAP101 Capsules at a dose of 60 mcg per day; IR calcifediol at a dose of 266 mcg on Day 1 and Day 29; high-dose cholecalciferol at a dose of 300,000 IU on Day 1 and Day 29; and paricalcitol at a dose of 1 mcg per day (possibly increasing to 2 mcg per day at Day 29) plus low-dose cholecalciferol 800 IU per day. If a significant difference in average weight among subjects by treatment group emerges during the course of the study, subjects may be placed into specific treatment groups rather than randomly assigned, in order to try and achieve more balance in the treatment groups by body weight.

The subjects will be housed in a phase 1 unit for approximately 14 to 26 hours at the beginning of the study and on study Day 29 to provide the blood samples required for a detailed determination of the PK profiles for serum calcifediol (25D₃) **CCI**

CCI

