4 STUDY POPULATION SELECTION

4.1 Study Population

The target population for this study is subjects at least 18 years old diagnosed with SHPT, stage 3 or 4 CKD and VDI (serum total 25-hydroxyvitamin D <30 ng/mL).

Approximately 160 patients will be screened to enroll approximately 80 eligible subjects, approximately 20 per treatment arm.

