7.2 Treatment Period

7.2.1 Visit 4 (Day 1)

Randomization will occur at the start of this visit.

- Subjects admitted into the phase 1 unit (for approximately 14 to 26 hours) after an overnight fast.
- Subjects will receive standardized meals while housed in the phase 1 unit. These meals will contain approximately 400 mg of elemental calcium and will be administered at approximately 2 (breakfast), 6 (lunch), and 10 (dinner) hours post-dose.
- Review of concomitant medications
- VS assessment
- Blood samples will be drawn from subjects housed in the phase 1 unit at approximately 6:00 a.m. ($t=$ ~2 hours), and 8:00 a.m. ($t=$ ~0 hours) and precisely (plus or minus 5 minutes, with exact time noted) at $t=$ 2, 4, 6, 12 and 24 hours (for subjects opting overnight stays), post-dose for the following analyses:
 - Chemistry (partial panel)

CC1

- Serum calcifediol, CC1
- Additional blood samples will be drawn from subjects housed in the phase 1 unit at approximately 8:00 a.m. ($t=$ ~0 hours) and precisely (plus or minus 5 minutes, with exact time noted) at $t=$ 12 and 24 hours (for subjects opting overnight stays) post-dose for the following analysis:

CC1

 - AE assessments will be completed at each timed blood draw (n=6)
 - Subjects take first dose of study drug with a sufficient quantity of a non-alcoholic beverage to enable swallowing of the capsules immediately after the $t=$ 0 blood draw, with the exact time of dosing noted.

CC1

[REDACTED]

- Subjects will be discharged from the phase 1 unit after the blood draw at 12 hours post-dose unless Subject chooses to stay overnight. Subjects opting to remain in the phase 1 unit for overnight will have 24 hour read completed. Those who do not opt to stay overnight, advance to Visit 5.
- Balance of monthly study drug supply dispensed at discharge to subjects assigned to CTAP101 Capsules and paricalcitol capsules plus low-dose cholecalciferol.

[figure not shown]

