9.2 Determination of Sample Size

No formal sample size estimation has been performed for the study.

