#### 3.3 Study Design

This is a phase 4, single- or multi-center, open-label study to evaluate the comparative safety, efficacy, and PK and **CCI** profiles of CTAP101 Capsules, IR calcifediol, high-dose cholecalciferol, and paricalcitol plus low-dose cholecalciferol **CCI** in male and female subjects at least 18 years of age with stage 3 or 4 CKD and VDI. The study will be conducted at up to 3 sites within the United States. Subjects (approximately 20 per arm) will receive the following treatments:

- 1) CTAP101 Capsules (30 mcg/capsule), 60 mcg by the oral route, once daily for 56 days;
- 2) Calcifediol IR (266 mcg/capsule), 266 mcg by the oral route, on Days 1 and 29;
- 3) Cholecalciferol (50,000 IU/capsule), 300,000 International Units (IU) by the oral route (6 capsules), on Days 1 and 29; and,
- 4) Paricalcitol (1 mcg/capsule) plus cholecalciferol (800 IU/capsule), 1 or 2 mcg plus 800 IU by the oral route, once daily for 56 days.

After 4 weeks of treatment, subjects who are receiving paricalcitol will double the dose to 2 mcg plus cholecalciferol 800 IU once daily in the morning before breakfast if all of the following conditions are met: the plasma iPTH has not decreased by at least 30% from

pretreatment BL and remains above 70 pg/mL, corrected serum total calcium is <9.8 mg/dL, and serum phosphorus is <5.5 mg/dL. Subjects who are receiving CTAP101 Capsules, IR calcifediol, or cholecalciferol (300,000 IU) will not undergo upward dose titration.

Subjects will reduce the dose of study drug per the following schedule if any of the following conditions are met: plasma iPTH is confirmed to be <30 pg/mL, corrected serum total calcium is confirmed to be >10.3 mg/dL, or serum phosphorus is confirmed to be >5.5 mg/dL.

Dose reduction (if needed):

CTAP101: decrease to 30 mcg per day (from 60 mcg per day)

IR calcifediol: hold Day 29 dose

Cholecalciferol 300,000 IU: hold Day 29 dose

Paricalcitol: decrease dose to 1 mcg per day (from 2 mcg per day)

Cholecalciferol 800 IU will not be adjusted

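### One published block size of 4 for four arms, in an open-label trial, makes the fourth assignment certain to anyone who has seen the first three

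*Protocol*

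**What the plan says.** Protocol 5.4 sets the method: "Randomization will be accomplished in blocks of 4 subjects in a 1:1:1:1 ratio". Protocol 9.3 and SAP 3.1 give the same single block size. No other size is mentioned, and nothing says that the size is withheld from sites.

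The Protocol synopsis describes the design: "This is a phase 4, multi-center, 4-arm, open-label study". SAP 3.3 calls it a "single- or multi-center, open-label study" and adds: "The study will be conducted at up to 3 sites within the United States". The Protocol speaks of multiple sites and sets no upper limit.

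On size, Protocol 4.1 says: "Approximately 160 patients will be screened to enroll approximately 80 eligible subjects, approximately 20 per treatment arm". Protocol 9.2 adds: "No formal sample size estimation has been performed for the study".

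On timing, Protocol 7.2.1 says of Visit 4 (Day 1): "Randomization will occur at the start of this visit". On eligibility, Protocol 5.4 says: "Laboratory assessments obtained at Visits 2-3 will not be considered in the determination of enrollment eligibility". Protocol 9.3 differs: there the Visit 2 results do count and only those of Visit 3 do not. The two sections need to be reconciled, but in both the deciding laboratory samples are taken before Visit 4.

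The readable text does not say whether blocks run within site or on one list across sites, who holds the list, or how the next assignment is concealed. SAP Appendix A lists a randomization schedule among the study appendices but does not describe its custody.

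**The concern.** When the block size equals the number of arms, every block is a permutation of the four treatments. The regimens differ openly (daily capsules against one dose on Day 1 and one on Day 29), so staff learn each assignment as soon as it is made. A person who has seen the first three in a block knows the fourth; a person who has seen two has the third narrowed to two arms.

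Staff could act on this between screening and Visit 4. Consent and screening are past by then, so the exposure lies in which eligible subject is brought to Visit 4, and in what order. Some judgement remains in that interval: entry criteria are reviewed again at Visits 2 and 3, exclusions 6 and 7 rest on the investigator's opinion, and the washout can be extended.

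At stake are the comparisons between treatments. Protocol 3.2 names comparison of safety and efficacy across the four regimens as a principal aim. SAP 7.3 plans least-squares differences with 95% confidence intervals and P values for calcifediol PK parameters, adjusted for baseline calcifediol only. Selection on CKD stage, comorbidity or expected adherence would not be adjusted for. With about 20 subjects per arm, a few steered subjects could move a group summary.

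**Working it through.** **Inputs.** Four arms, 1:1:1:1, fixed block of 4 (Protocol 5.4 and 9.3, SAP 3.1); about 80 subjects, about 20 per arm (Protocol 4.1). No power, effect size or SD enters.

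**The plan's own figure.** 80 / 4 arms = 20 per arm, and 80 / 4 per block = 20 complete blocks. This agrees with the plan. The documents state no predictability figure.

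**Case A: the observer sees every earlier assignment in the block** (single site, blocks within site, or allocations shared between sites). At position k, 4 − (k − 1) arms remain, all equally likely, so P(correct) = 1/(5 − k):

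- positions 1 to 4: 1/4, 1/3, 1/2, 1
- mean: (0.2500 + 0.3333 + 0.5000 + 1.0000)/4 = 0.521, or 41.7 of 80, against 0.25 (20 of 80) under simple randomisation
- certain assignments: one per block = 20 of 80 = 25%

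**Case B: one concealed list across S sites.** Assumptions: equal random recruitment, each site sees only its own subjects, and staff know where blocks begin (generous to the observer). The number m of earlier subjects in the block enrolled at the same site is Binomial(k − 1, 1/S), and P(correct) = E[1/(4 − m)].

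| Position | S = 2 | S = 3 |
|---|---|---|
| 1 | 0.250 | 0.250 |
| 2 | 0.292 | 0.278 |
| 3 | 0.354 | 0.315 |
| 4 | 0.469 | 0.370 |
| Mean | 0.341 | 0.303 |

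The fourth assignment is certain only if the same site enrolled the previous three, with probability (1/S)³:

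- S = 2: 0.125 × 20 blocks = 2.5 of 80, about 3%
- S = 3: 0.037 × 20 blocks = 0.7 of 80, about 1%

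**Effect of changing the block size, under Case A.** The fixed sizes are exact. The mixed sizes were simulated over 80 subjects, with sizes drawn with equal probability and an observer who knows the set of sizes and all earlier assignments.

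| Scheme | Certain | Best guess correct |
|---|---|---|
| Fixed 4 (plan) | 25% | 52.1% |
| Fixed 8 | 14.3% | 47.0% |
| Mixed 4/8 | 7.4% | 48.4% |
| Mixed 4/8/12 | 3.3% | 46.1% |

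Mixing the sizes removes most of the certainty but only a small part of the average advantage. Concealing the list across sites does more for the average, as Case B shows.

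**The case against.** The strongest reply is that block size alone reveals nothing. Foresight needs knowledge of the earlier assignments in the same block, and no section says that blocks run within site. The Protocol describes several sites, and its weight-balancing rule uses means over all subjects entered so far, which fits trial-wide assignment. On one concealed list, certain assignments are about 1% to 3%. This stands. The 25% is a worst case: possible, because SAP 3.3 allows a single centre, but not established. A reader might infer from block size and open-label treatment that site staff will know every fourth assignment; the documents do not support that without the further condition. The limit of 3 sites is also in the SAP only.

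Second, the study is mainly descriptive. No efficacy endpoint is designated, many entry criteria are numerical laboratory limits, and the one readable model-based comparison is exploratory and on laboratory-measured concentrations. This lowers the stakes without removing them. Laboratory measurement guards against biased assessment, not against selecting who enters an arm, and the relatedness of adverse events is judged by investigators who know the treatment. A reader might also infer that the comparisons are in fact biased. Nothing in the documents shows that, or a direction.

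Third, varying the blocks lowers average guess accuracy only from 52% to 46%, and does nothing once the weight-based procedure in Protocol 5.4 and 9.3 replaces block randomisation. Both statements are correct. The benefit is mainly in the certain assignments, and the weight procedure is a separate and more predictable route.

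**Conclusion.** The point holds in conditional form. The plan fixes and publishes a block size that makes the fourth assignment in each block certain, and the third an even guess, to anyone who knows those before it. The range is 20 of 80 certain (25%) with 52% guess accuracy if the sequence is visible at the site, down to about 3% or 1% certain with 34% or 30% accuracy on one concealed list over 2 or 3 sites. The lower figures rest on the assumptions of equal random recruitment and of sites not sharing allocations. The documents do not settle where in the range the trial lies. All figures apply only while block randomisation is in force.

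This is an avoidable opportunity for selection bias in the comparisons the plan makes. It is a minor point, worth correcting because the correction is cheap.

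**What to change.** For assignments not yet made, generate a list with randomly varying block sizes in multiples of 4, such as 4, 8 and 12, and hold it where sites cannot see it. Remove the block size from Protocol 5.4 and 9.3 and, until enrolment ends, from SAP 3.1; it can be reported afterwards. State in the protocol who holds the list, how each assignment is released at Visit 4, and whether blocks run within site.

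In the worst case this cuts certain assignments from 25% to about 3% and best-guess accuracy from 52% to about 46%.

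The cost is a new list and a protocol amendment. If enrolment stops inside a block of 12, which holds 3 of each arm, arm sizes can differ by up to 3, against 1 with blocks of 4; with separate site lists these differences can add up. The change does not deal with the weight-based assignment procedure, which needs its own correction.
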